### 5.1.3 Dosing and Administration of IgPro20 and Placebo

The investigator (or delegate) will dispense or administer IMP only to subjects included in this study following the procedures set out in this study protocol. Information on the dosing characteristics of IMP is provided in Table 5.

**Table 5** **Investigational Medicinal Product Dosing Characteristics**

SC Infusion Parameter	IgPro20	Placebo
Route	SC	SC
Anatomical location	Abdomen, thigh, upper arm, and/or lateral hip	Abdomen, thigh, upper arm, and/or lateral hip
Total infusion volume	Dependent on body weight (eg, 80 kg subject, 200 mL)	Dependent on body weight (eg, 80 kg subject, 200 mL)
Infusion duration	Volume and number of infusion sites dependent	Volume and number of infusion sites dependent

SC = subcutaneous.

All IMP in the study will be administered by SC infusions as weekly doses of 0.5 g/kg. At least the first SC infusion for Week 1 and Week 2 must be administered during the study visit at the investigational site to allow for training and confirmation of appropriate SC infusion technique. After Week 1 and Week 2, all weekly SC infusions will be self-administered at home. The SC infusions can be performed on 1, 2, 3, or 4 days each week and more than 1 infusion can be performed on a single day. It is preferred that the SC infusions be performed in a similar way throughout the study, ie, the same number of infusions and the same number of days each week after Week 2; however, the dosing regimen can be adjusted during the study in case of intolerance or inconvenience. All SC infusions for the previous week must be performed before the following study visit, eg, all Week 4 SC infusions performed before the day of the Week 5 Visit. Body weight will be measured at every study visit and changes in body weight > 2 kg will require a dose volume adjustment. The total dosing volume of IMP will be managed by the interactive response technology (IRT) system. Preparation instructions are provided in the IMP manual.

## Subcutaneous Infusion Dosing Regimen Example:

Total dose volume per week needed for 80 kg subject = 200 mL. See [Appendix 15](#) for weekly weight-based dosing regimen table.

Infusion dosing options may include but are not limited to the following:

- Total volume can be delivered on 1 day using 4 infusions of 50 mL
- Total volume can be delivered on 2 days using 2 infusions of 50 mL each day
- Total volume can be delivered on 3 days using 1 infusion of 50 mL each for 2 days and 2 infusions of 50 mL on the third day
- Total volume can be delivered on 4 days using 1 infusion of 50 mL each day

The SC infusions should be performed at appropriate infusion sites (eg, on the abdomen, thighs, upper arm, and/or lateral hip). The number of infusion sites is dependent upon the total volume administered. The maximum rate and the maximum volume per infusion site should not be exceeded and increases up to the maximum should be done gradually as tolerated.

## Subcutaneous Infusion Volume and Rate of Infusion:

- **Volume (mL/Site):**  $\leq 20$  for Week 1 and  $\leq 50$  as tolerated for all subsequent study weeks
- **Rate of infusion (mL/hour/site):**  $\leq 20$  for Week 1 and  $\leq 50$  as tolerated for all subsequent study weeks

## *Subcutaneous Treatment Training*

Every randomized subject (and their caregiver, if applicable) will receive instructions on the SC infusion pump and SC infusion technique. Training on SC infusion through the use of video and/or verbal instruction should first be discussed with the subject during Screening to familiarize the subject with the SC infusion procedure before randomization. Site staff should recommend the weekly dosing regimen based on the subject's weight, ie, number of SC infusions needed to deliver the total volume in 1 week. The Crono Pump should be programmed by the site staff with the correct volume based on body weight before the study visit ends. The programmed pump volume should be confirmed at every study visit.

The subject will be trained at the study site at the Week 1 Visit and Week 2 Visit by the site staff. Retraining of the subject or caregiver at the site is permitted for an additional 2 weeks

(Week 3 and Week 4), only if the subject or caregiver experiences difficulty with the SC infusion technique. Additional trainings needed beyond Week 2 will be documented in the eCRF. No other study procedures are required to be performed at these additional SC infusion trainings. If the subject or caregiver still is not able to administer the SC infusions at home by Week 4, the subject will be withdrawn from treatment and encouraged to continue study assessments to Week 25 (EOP1).

Detailed information on the home storage, preparation, and SC infusion of IMP will be provided in the IMP manual.

The CRONO S-PID 50 Pump will be provided to deliver the SC infusions to the subject. Refer to the IMP manual and the CRONO Pump user guide for further details on the device.

### **5.1.3.1 Dosing Modification**

Modifications of IMP dose are not permitted.

### **5.1.3.2 Treatment Compliance**

Subjects will record details of their infusion in the diary including whether the caregiver assisted in the SC infusion. In addition, subjects will bring all of their used/partially used vials of IMP to the study site at every study visit. Treatment compliance will be monitored based on review of the diary data and the number of returned vials, the results of which will be documented.

### **5.1.3.3 Overdose**

Overdose is defined as the accidental or intentional infusion or ingestion of any dose of a product that is considered excessive. The effects of any potential overdose with IgPro20 have not been studied. See [Section 9.6.5](#) for IMP overdose reporting requirements.

## **5.1.4 Packaging, Labeling, Supply and Storage**

### **5.1.4.1 Packaging and Labeling**

IMP will be packaged and labeled according to current ICH GMP and GCP guidelines and national legal requirements. Specific details regarding packaging of IMP are provided in the IMP manual.

### 5.1.4.2 Supply and Storage

IMP will be supplied to the study sites by CSLB or delegate.

Refer to [Section 5.1.1](#) and [Section 5.1.2](#) for IMP site storage instructions. Subjects will be required to place IMP in home refrigerators for storage. Storage details will also be included in the IMP manual provided to the sites and the subjects.

## 5.2 Accountability and Destruction

IMP must be used only as directed in the clinical study protocol.

The investigator (or delegate) will confirm receipt of all shipments of IMP (IgPro20 and placebo) in the IRT system. All supplies of IMP must be accounted for throughout the study. Records for the delivery of IMP to the study site, the inventory at the study site, the use by each subject, and the destruction or return of IMP to CSLB/designee must be maintained by the investigator (or delegate) using the appropriate form or IRT system. The investigator (or delegate) must provide reasons for any discrepancies in drug accountability.

For Japan sites only, drug inventory and accountability logs/reports must be dated and signed by the head of the medical institute or the study drug storage manager (if assigned by the head of medical institute). The study drug storage manager may delegate the tasks to the responsible hospital pharmacists.

Further details regarding accountability and destruction of IMP are provided in the IMP manual.

## 5.3 Other Interventions

### 5.3.1 Oral Rescue Corticosteroid Treatment

In the event of clinical worsening (eg, subject meets DOW criteria) between Week 9 and Week 25, the investigator may decide that the subject requires oral rescue corticosteroid treatment for recovery. Intravenous pulse rescue corticosteroid treatment is not permitted.

In this case, the following guidance applies:

- 1 Oral rescue corticosteroid treatment should be given only if DOW criteria are met.
- 2 The earliest that oral rescue corticosteroid treatment can be given is Week 9, to allow for IMP steady state to be achieved. The DOW consists of meeting 1 of the following 3 criteria on 2 consecutive study visits at least 2 weeks apart, up to Week 25:

- a) Physician Global Disease Activity Assessment VAS worsening  $\geq 2$  cm\* and MMT-8 worsening  $\geq$  absolute 10%, - OR -
- b) Extramuscular Global Assessment VAS worsening  $\geq 2$  cm, - OR -
- c) Any 3 of 6 CSMs (see [Section 3.3.1](#)) worsening by  $\geq$  absolute 20%
  - \* If baseline Physician Global VAS is 8 to 10, then any worsening on Physician Global VAS is acceptable as long as MMT-8 criterion is met.

3 The rescue oral corticosteroid (prednisolone equivalent) treatment should be provided as per the Treating Physician's (see [Table 7](#)) standard of care but should not exceed 1 mg/kg/day for up to 5 days.

4 It is recommended that after oral rescue corticosteroid treatment, the oral corticosteroid dose be returned to Baseline dose by Week 25, if clinically possible.

Clinical worsening according to DOW is finished at the first subsequent study visit where none of the criteria are met. A potential next DOW and possible rescue oral corticosteroid treatment can start only after the end of the preceding DOW.

Oral rescue corticosteroid treatment is not permitted in Study Period 2. During Study Period 3, the use of additional oral corticosteroid treatment is permitted. Prior to increasing corticosteroids, investigators should verify that subjects are still benefiting from treatment with IgPro20.

#### ***Consequence of oral rescue corticosteroid treatment during Study Period 1***

The subject will be classified as a non-responder at Week 25 but will continue the study as long as the subject remains on IMP treatment.

### 5.3.2 Concomitant Oral Corticosteroid Tapering

The permitted  $\leq 20$  mg/day concomitant oral corticosteroid (prednisolone equivalent) dose must be tapered starting at Week 17 if the subject has demonstrated clinically relevant improvement, ie,  $\geq 2$  cm improvement on the 10-cm Physician Global Disease Activity Assessment VAS. The taper regimen to be followed depends on the subject's previous stable corticosteroid dose:

- a) If stable dose is 11 to 20 mg/day oral prednisolone equivalent, decrease dose by 2.5 mg/day every 2 weeks, as tolerated, to 10 mg, then by 1 mg/day every 2 weeks as tolerated
- b) If stable dose is  $\leq 10$  mg/day, taper by 1 mg/day every 2 weeks as tolerated

If lowering the dose of corticosteroids results in an increase in symptoms that does not meet criteria for oral corticosteroid rescue treatment but in the judgement of the Treating Physician requires response, it is permissible to increase the dose of concomitant oral corticosteroid to up to 125% of the Baseline corticosteroid dose; only an increase to doses greater than 125% of the Baseline corticosteroid dose following corticosteroid taper starting at Week 17 will be considered a "rescue" corticosteroid dose. Once clinical stabilization has occurred, the taper schedule will resume (ie, taper will continue to a dose in which the subject remains stable).

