## 7.2 Permitted Therapies

The following therapies are PERMITTED during the study (note: this list is not intended to be all inclusive) provided a stable dose/regimen has been achieved according to the designated time period (in parentheses) before Baseline:

- Prednisolone equivalent ( $\leq 20$  mg/day, except for oral rescue corticosteroid treatment [Table 6]), topical corticosteroids (low to medium potency), inhaled corticosteroids, topical immunosuppressants, physiotherapy (1 month). Taper of concomitant oral corticosteroid dose is required starting at Week 17 if the subject has demonstrated clinically relevant improvement (see [Section 5.3.2](#)). Monitoring for corticosteroid side effects should continue (see [Section 8.1.2.1](#)).

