**Table 6** **Corticosteroid Dose Equivalency**

Corticosteroid	Equivalent Dose	Corticosteroid	Equivalent Dose
Prednisolone	20 mg	Betamethasone	2.4 mg
Prednisone	20 mg	Dexamethasone	3.0 mg
Methylprednisolone	16 mg	Hydrocortisone	80 mg
Triamcinolone	16 mg	Cortisone	100 mg

Source: [Farinde, 2019](#); values in source were multiplied by 2 to equal 20 mg prednisolone dose.

- Antimalarial agents, eg, hydroxychloroquine, chloroquine (3 months)
- Systemic immunosuppressives or disease-modifying antirheumatic drugs, eg, azathioprine, methotrexate, mycophenolate, cyclosporine, tacrolimus (3 months)

Doses of stable permitted therapy (including corticosteroids) may be reduced or discontinued after enrollment because of side effects, abnormal laboratory values, or concurrent illness. No other change to permitted concomitant therapy, with the exception of taper of corticosteroid dose starting at Week 17 (see [Section 5.3.2](#)), is allowed during Study Periods 1 and 2.

In Study Period 3, doses of stable concomitant medication may be decreased based on subject status.

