## 8.4 Prior and Concomitant Therapies

All medications taken by a subject within 3 months before Baseline are considered prior therapy and must be documented in the eCRF.

Previous medications and therapies for DM that the subject has received within 1 year before Baseline must be documented in the eCRF. If possible, all available data regarding the subject's treatment with IgG therapy since being diagnosed with DM should be recorded in the subject's eCRF.

All drugs and/or procedures currently being administered to a subject at the time of signing informed consent, and which continue to be taken in addition to IgPro20 or placebo during the study, as well as drugs and/or procedures initiated after the first infusion of study product, are regarded as concomitant therapies and must be documented as such in the eCRF.

Any prohibited dose adjustments in permitted concomitant therapies (see [Section 7.2](#)) will lead to withdrawal from treatment.

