### 10.4.2.3 Primary Efficacy Endpoint

The primary endpoint is the responder status in each treatment sequence based on TIS assessments at Weeks 17, 21, and 25. Following the estimand described in [Section 10.4.2.2](#), a responder is defined as a subject with a TIS  $\geq 20$  points at Week 25 and at least 1 of the previous scheduled visits (Week 17 or Week 21), who completes 24 weeks of randomized IMP treatment without the use of rescue corticosteroid treatment. Therefore, for subjects who do not withdraw from IMP or the study for reasons that are related to the Ukraine war before Week 25, non-responders will include subjects who meet any 1 of the following:

- TIS  $< 20$  points at Week 25
- TIS  $< 20$  points at both Weeks 17 and 21
- Withdraw from treatment or the study or receive rescue corticosteroid treatment before Week 25

To ensure that the treatment effect is not confounded by the intercurrent event of premature withdrawal from IMP or the study due to the Ukraine war, the hypothetical strategy is applied for this intercurrent event to quantify the treatment effect in the absence of the Ukraine war [[Meyer et al, 2020](#); [Collins et al, 2020](#)]. For subjects who do withdraw from IMP or the study for reasons which are related to the Ukraine war before Week 25, scheduled TIS assessments after withdrawal are missing. These missing values can be considered missing at random and multiple imputation will be used to derive the hypothetical post-intercurrent event TIS values and the corresponding response variables assuming that the subjects with missing TIS values continue in the same way as similar subjects in the study who did not withdraw prematurely. Multiple imputation is a simulation based approach where missing values are replaced by multiple Bayesian draws from the conditional distribution of missing data given the observed data and covariates, creating multiple completed data sets. The completed data sets can then be analyzed using standard methods (see [Section 10.4.2.3.1](#)). Note: If no TIS values are available for the subject for any post-randomization visit during Study Period 1, the subject will be excluded from the mITT analysis set (see [Section 10.3](#)).

Details of the multiple imputation process for TIS values and derivation of the responder status are provided below:

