## 10.2 Analysis of Primary Endpoint

The primary endpoint is the responder status in each treatment sequence based on TIS assessments at Weeks 17, 21, and 25. Following the estimand described in Section 10.1, a responder is defined as a subject with a TIS  $\geq 20$  points at Week 25 and at least at 1 of the previous scheduled visits (Week 17 or Week 21) who completes 24 weeks of randomized IMP treatment without the use of oral rescue corticosteroid treatment.

Therefore, for subjects who do not withdraw from IMP or the study for reasons which are related to the Ukraine war before Week 25, non-responders will include subjects who meet any 1 of the following:

- TIS  $< 20$  points at Week 25
- TIS  $< 20$  points at both Weeks 17 and 21
- Withdraw from treatment or the study or receive oral rescue corticosteroid treatment before Week 25 (Note: for subjects with corticosteroid taper starting at Week 17, only an increase to doses greater than 125% of the Baseline corticosteroid dose following corticosteroid taper starting at Week 17 will be considered a “rescue” corticosteroid dose)

To ensure that the treatment effect is not confounded by the intercurrent event of premature withdrawal from IMP or the study due to the Ukraine war, the hypothetical strategy is applied for this intercurrent event to quantify the treatment effect in the absence of the Ukraine war [Meyer et al, 2020; Collins et al, 2020]. For subjects who withdraw from IMP or the study for reasons which are related to the Ukraine war before Week 25, scheduled TIS assessments after withdrawal are missing. These missing values can be considered missing at random (MAR) and multiple imputation will be used to derive the hypothetical post-intercurrent event TIS values and the corresponding response variables assuming that the subjects with missing TIS values continue in the same way as similar subjects in the study who did not withdraw prematurely. Multiple imputation is a simulation based approach where missing values are replaced by multiple Bayesian draws from the conditional distribution of missing data given the observed data and covariates, creating multiple completed data sets. The completed data sets can then be analyzed using standard methods. Note: If no TIS values are available for the subject for any post-randomization visit during Study Period 1, the subject will be excluded from the mITT analysis set (see Section 6).

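### After taper, Protocol 5.3.2 permits corticosteroid doses that can exceed the 20 mg/day cap in 7.2, and applying 8.4 to such a dose before Week 25 would make a possible responder a non-responder

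*Protocol*

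**What the plan says.** Protocol 5.3.2 requires the concomitant oral corticosteroid to be tapered from Week 17 in subjects with clinically relevant improvement. If symptoms then increase without meeting the rescue criteria, and the Treating Physician judges that a response is needed, "it is permissible to increase the dose of concomitant oral corticosteroid to up to 125% of the Baseline corticosteroid dose". No absolute limit in mg is attached. SAP 10.2 carries the matching threshold into the non-responder definition: "only an increase to doses greater than 125% of the Baseline corticosteroid dose following corticosteroid taper starting at Week 17 will be considered" a rescue dose. An increase to 125% or less therefore leaves the subject able to be a responder.

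Protocol 7.2 lists prednisolone equivalent among the permitted therapies at up to 20 "mg/day, except for oral rescue corticosteroid treatment". Below Table 6, the same section restricts changes during Study Periods 1 and 2: "No other change to permitted concomitant therapy, with the exception of taper of corticosteroid dose starting at Week 17", followed by a cross-reference to 5.3.2.

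Protocol 8.4 states the consequence: "Any prohibited dose adjustments in permitted concomitant therapies", judged by reference to 7.2, "will lead to withdrawal from treatment".

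Protocol 10.4.2.3 counts as non-responders those who "Withdraw from treatment or the study or receive rescue corticosteroid treatment before Week 25". Protocol 4.3.5 and SAP 10.1 and 10.2 agree, with the exception of withdrawals related to the Ukraine war.

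**The concern.** A dose between 20 mg/day and 125% of Baseline is, by the wording of 5.3.2, not rescue. It therefore cannot use the only exception that 7.2 gives to its 20 mg/day figure. One section says the dose may be given. The other two, read literally, put it outside the permitted range and attach withdrawal from treatment to it.

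This bears on the primary endpoint because IMP withdrawal before Week 25 is treatment failure in the primary estimand. A site following 5.3.2 keeps the subject on IMP, and the subject can still qualify on TIS. A site applying 7.2 with 8.4 withdraws the subject, who is then a fixed non-responder whatever the TIS shows. The classification would depend on which section the site read, not on the subject's course.

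**Working it through.** **Inputs**
- Ceiling after taper that is not rescue: 1.25 × Baseline dose d (Protocol 5.3.2; same threshold in SAP 10.2).
- Entry limit: d ≤ 20 mg/day prednisolone equivalent (Protocol 4.1.1, inclusion criterion 6).
- On-study cap: 20 mg/day, rescue excepted (Protocol 7.2).
- Taper for a stable dose of 11 to 20 mg/day: 2.5 mg/day every 2 weeks down to 10 mg (Protocol 5.3.2).

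**Step 1: where the ceiling passes the cap.** 1.25 × d > 20 when d > 20 / 1.25 = 16 mg/day.

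| Baseline d (mg/day) | 1.25 × d | Amount above 20 |
|---|---|---|
| 10 | 12.5 | none |
| 15 | 18.75 | none |
| 16 | 20.0 | none |
| 17.5 | 21.875 | 1.875 |
| 18 | 22.5 | 2.5 |
| 20 | 25.0 | 5.0 |

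The band of conflict runs from just above 20 mg/day to 1.25 × d, for 16 < d ≤ 20. At a Baseline of 16 or less it is empty.

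**Step 2: what has to happen.** A Baseline above 16 mg/day is not enough. The re-escalated dose must itself exceed 20 mg/day, which is above the subject's own Baseline unless that was exactly 20 (and then any dose above Baseline qualifies). At a Baseline of 17.5, for example, the dose must exceed 20 / 17.5 = 114% of Baseline. Re-escalation back to Baseline or below raises no conflict.

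**Step 3: whether it can fall within the primary window.** A subject on 20 mg/day who starts taper at Week 17 goes to 17.5 (Week 17), 15 (Week 19), 12.5 (Week 21) and 10 (Week 23). That leaves 25 − 17 = 8 weeks in which symptoms could increase and the dose be raised before Week 25. The case is possible.

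**Step 4: the sections side by side, for a dose above 20 mg/day and at most 1.25 × d**
- 5.3.2: permitted, not rescue.
- 7.2, 20 mg/day limit: exceeded, and the rescue exception does not apply.
- 7.2, sentence on other changes: it points to 5.3.2, so it can be read as covering re-escalation within the taper procedure. It is not a clear conflict by itself.
- 8.4: withdrawal from treatment, if the dose is judged prohibited under 7.2.
- 4.3.1, list of mandatory reasons to discontinue IMP: this reason is not listed. Withdrawal therefore rests on the 7.2 cap together with 8.4.
- 10.4.2.3 and SAP 10.2: possible responder if kept on IMP, non-responder if withdrawn before Week 25.

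**The case against.** The strongest reply is that 8.4 reaches only prohibited adjustments, while 5.3.2 expressly allows this one, and a specific rule should prevail over a general cap. Several passages support it. Both relevant parts of 7.2 refer to 5.3.2. Section 5.3.2 places re-escalation inside the taper procedure, with taper resuming after stabilization. Section 3.1 describes the 20 mg/day figure as a Baseline dose, and the 7.2 list is introduced by stability before Baseline, so the cap can be read as an entry limit. Section 7.3 does not list oral doses above 20 mg/day among the prohibited therapies. The literal reading also has an odd result: rescued subjects may receive up to 1 mg/kg/day for up to 5 days (5.3.1) and continue IMP, while a smaller non-rescue dose would end it.

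This shows that the texts can be harmonized, and it disposes of the claim that the sentence on other changes is a second contradiction. It does not remove the remaining conflict. Section 7.2 lists what is permitted during the study, states a cap, and excepts rescue only. Nothing tells a site that the 125% rule overrides it.

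The reply is also right that the SAP is not silent. Any IMP withdrawal before Week 25 unrelated to the war is non-response, and an increase to 125% or less after taper is not rescue. The existing sensitivity analyses in SAP 10.2.1 do not clearly settle this case, however. Analyses (2) and (3) concern subjects withdrawn from the study. Analysis (5), on increased corticosteroids without meeting the definition of worsening, has a title only and mentions neither the cap nor an 8.4 withdrawal.

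**Conclusion.** The conflict stands in a narrow form. For Baseline doses above 16 and up to 20 mg/day, a re-escalated dose actually above 20 mg/day and no more than 125% of Baseline is allowed by Protocol 5.3.2 and outside the cap in 7.2. It reaches the primary endpoint only if a site applies 8.4 before Week 25, and changes the result only if the subject would otherwise have been a responder.

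Three stronger readings are tempting but not supported:
- *Every subject above 16 mg/day is affected.* Taper, a symptom increase short of the rescue criteria, and an actual dose above 20 mg/day are all needed.
- *The protocol orders withdrawal in these cases.* Section 4.3.1 does not list the reason, and 5.3.2 can be read as taking the dose out of 8.4. The instruction is unclear, not uniformly opposite.
- *The trial loses power, mainly through IgPro20 responders.* Taper follows improvement, but the trigger here is a symptom increase during taper, and its distribution by arm is unknown. The documents do not give the distribution of Baseline doses or the frequency of re-escalation. Any power figure would rest on an invented count, and none is given here.

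What remains is a wording conflict with a possible effect of unknown, perhaps zero, size on individual responder classifications. It is worth correcting because the correction is cheap and must precede unblinding to be credible.

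**What to change.** 1. **Protocol.** Reconcile 5.3.2, 7.2 and 8.4 so that one statement governs re-escalated doses above 20 mg/day and says whether they trigger 8.4. Which rule applies is the sponsor's clinical decision.
2. **BDRM, before unblinding.** List any subject withdrawn from IMP before Week 25 solely for a dose that 5.3.2 permits, and any subject kept on IMP at a dose above 20 mg/day and within 125% of Baseline.
3. **SAP.** Keep the existing classification in 10.2 for the primary analysis. If the list is not empty, add one sensitivity analysis with the opposite classification: subjects kept on IMP become non-responders, and withdrawn subjects are classified from their available TIS data. Protocol 4.3.1 encourages subjects who stop IMP in Study Period 1 to stay until Week 25, so such data may exist. SAP 8.2.3 includes efficacy assessments made within 7 days after IMP discontinuation, so the new text must say that later ones are used here and how a missing Week 25 value is handled.

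The cost is a short protocol clarification, one BDRM listing and, at most, one small extra analysis. If the list is empty, no analysis is needed.
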